#### 11.6.3 Replication Competent Lentivirus Analysis

A replication competent lentiviral (RCL) assay will be performed on 5 mL of blood collected at Visit 1 (at any time up until 4 weeks prior to the scheduled administration date) and Visits 5, 6, 8, and 10, (collected at Visit 7 and 9 if visit is conducted in office) and then yearly thereafter for up to 15 years (as described in the Long-Term Follow-Up Section **7.5**). If all post-treatment RCL assays are negative during the first year (e.g., Weeks 4, 12, 16, 25, 32, and 52), collection of the yearly follow-up samples will be discontinued. The Long-Term Follow-Up blood samples can be collected remotely by the Subject's primary EB care physician. A positive RCL assay result must be recorded as an adverse event.

#### 11.6.4 C7 Antibody Assay

Subject serum will be collected at Screening and Visits 5, 6, 8, and 10 (collected at Visit 7 and 9 if visit is conducted in office) for the purpose of conducting a C7 antibody assay. Subject serum will be evaluated by indirect IF using monkey esophagus as a substrate. Western blot analysis

CONFIDENTIAL Page 52 of 75

Fibrocell Technologies RDEB Phase I/II Protocol Final Version 8.0, 29 Oct 2019

can be performed as needed. A positive C7 antibody assay result must be recorded as an adverse event.

CONFIDENTIAL Page 53 of 75

Final Version 8.0, 29 Oct 2019

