At a minimum, FDA and DSMB approvals are required for enrollment of pediatric subjects. Local oversight committees may also require approval.

Each phase of the study is divided into four (4) periods: Screening, Wound Monitoring, Treatment, and Long-Term Follow-Up. The Screening Period consists of entry criteria evaluations, the collection of one set of three 3-4 mm biopsies for FCX-007 manufacturing, and the identification and photography of potential target wounds. FCX-007 manufacturing requires about 4 months. This period is the Wound Monitoring Period. Subject target wounds may be imaged a minimum of two times (at least 4 weeks apart) during this period. The purpose of the imaging is to identify wounds with the most consistent wound areas that meet criteria, and to establish a baseline area that takes into account natural wound area variation. The Wound Monitoring Period is expected to have a duration of approximately four months; however, this period can extend beyond four months to accommodate patient scheduling, variations in manufacturing duration and protocol mandated delays (i.e. pauses due to staggered treatment).

After FCX-007 manufacturing is complete, Fibrocell (the Sponsor) and the Investigator will mutually agree on the date of receipt of FCX-007. The duration of the Treatment Period may fluctuate between two and four days to accommodate subject safety and scheduling. The Treatment Period visits (Day -2 to Day 2) will be scheduled so that the day of dosing (Day 0) is the day of receipt of FCX-007. Prior to dosing, wounds are identified that meet treatment criteria based on imaging results obtained. Up to three pairs of target wounds may be identified for each subject and the Investigator will pair the target wounds according to similarity in wound area.

One wound in each pair will receive FCX-007 and the other wound no treatment.

Safety and proof of mechanism evaluations are conducted during site visits at Visits 5 (Week 4), 6 (Week 12), 8 (Week 25) and 10 (Week 52), and unscheduled visits. Proof of mechanism will be monitored through assays conducted on biopsies taken from target wounds and areas of intact skin in which FCX-007 was administered.

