Proceeding to administration of FCX-007 after a stagger requires that the previous subject complete Week 4 evaluations and the Investigator must have received approval from the Data Safety Monitoring Board (DSMB) to continue the study prior to the next subject's FCX-007 administration.

At a minimum, FDA and DSMB approvals are required for enrollment of pediatric subjects. Local oversight committees may also require approval.

Each phase of the study is divided into four (4) periods: Screening, Wound Monitoring, Treatment, and Long-Term Follow-Up. The Screening Period consists of entry criteria evaluations, the collection of one set of three 3-4 mm biopsies for FCX-007 manufacturing, and the identification and photography of potential target wounds. FCX-007 manufacturing requires about 4 months. This period is the Wound Monitoring Period. Subject target wounds may be imaged a minimum of two times (at least 4 weeks apart) during this period. The purpose of the imaging is to identify wounds with the most consistent wound areas that meet criteria, and to establish a baseline area that takes into account natural wound area variation. The Wound Monitoring Period is expected to have a duration of approximately four months; however, this period can extend beyond four months to accommodate patient scheduling, variations in manufacturing duration and protocol mandated delays (i.e. pauses due to staggered treatment).

After FCX-007 manufacturing is complete, Fibrocell (the Sponsor) and the Investigator will mutually agree on the date of receipt of FCX-007. The duration of the Treatment Period may fluctuate between two and four days. The Treatment Period visits (Day -2 to Day 2) will be scheduled so that the day of dosing (Day 0) is the day of receipt of FCX-007. Prior to dosing, wounds are identified that meet treatment criteria based on imaging results obtained. Up to three pairs of target wounds may be identified for each subject and the Investigator will pair the target wounds according to similarity in wound area.

One wound in each pair will receive FCX-007 and the other wound no treatment.

Safety and proof of mechanism evaluations are conducted during site visits at Visits 5, 6, 8 and 10 (weeks 4, 12, 25, 52), and unscheduled visits. Proof of mechanism will be monitored through assays conducted on biopsies taken from target wounds and areas of intact skin in which FCX-007 was administered.

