# 3.4 Estimated Study Duration

The duration is about 20 months per subject, including the Screening, Wound Monitoring and Treatment Periods. Recruitment is anticipated to take approximately 8 months, resulting in total study duration of approximately 28 months. The end of Treatment Period Visit is scheduled to occur at the end of the 12-month treatment phase. Safety data will continue to be collected by clinic visit or telephone contact approximately every 1 year for at least 15 years after the treatment phase.

CONFIDENTIAL Page 19 of 75

Final Version 8.0, 29 Oct 2019

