### 4.2 Exclusion Criteria

Subjects will be excluded from the study if any of the following criteria are met:

- 1. Medical instability limiting ability to travel to the investigative center.
- 2. Active infection with HIV, hepatitis B or hepatitis C, as determined by hepatitis B surface antigen screening, detection of hepatitis C antibodies, or positive result of hepatitis C PCR analysis.
- 3. The presence of antibodies to the basement membrane of monkey esophagus by indirect immunofluorescence using the subject's serum.
- Evidence of systemic infection.
- 5. Current evidence of metastatic squamous cell carcinoma at the site to be injected.
- 6. Known allergy to any of the constituents of the product.
- 7. Active drug or alcohol addiction.
- 8. Hypersensitivity to anesthesia chosen (lidocaine/prilocaine cream, moderate sedation, or general anesthesia).
- 9. Receipt of a chemical or biological study product for the specific treatment of RDEB in the past six months
- 10. Women who are pregnant or breast-feeding.
- 11. Any clinically significant abnormal laboratory result from Day -2 (Grade 2 or higher on the National Cancer Institute [NCI] toxicity scale), except for the following:
  - a. Albumin < 2.5 g/dL,
  - b. Leukocytes > 20K/uL,
  - c. Hemoglobin < 7.5 g/dL
- 12. Clinically significant abnormalities (Grade 2 or higher on the NCI toxicity scale) identified through medical history and physical examination at Day 0, with the following exceptions:
  - a. Anorexia, can enroll up to Grade 4 (inclusive)
  - b. Constipation, can enroll up to Grade 2 (inclusive)
  - c. Dysphagia, can enroll up to Grade 4 (inclusive)
  - d. Keratitis, can enroll up to Grade 4 (inclusive)
  - e. Bone pain, can enroll up to Grade 2 (inclusive)

CONFIDENTIAL Page 21 of 75

Final Version 8.0, 29 Oct 2019

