# 6.1 Manufacturing

### 6.1.1 FCX-007 Manufacturing

FCX-007 will be manufactured from one set of three 3-4 mm biopsies obtained at the Screening Visit. The biopsies will be placed into sterile phosphate buffered saline (PBS), and shipped at 2-8°C immediately to the manufacturing facility. Upon receipt of the biopsies, FCX-007 will be manufactured by gene modification and expansion of dermal fibroblasts obtained from the biopsy. The tissue will be digested with enzymes to release the fibroblasts, which will then be seeded into a tissue culture vessel. The cells will be expanded, transduced with INXN-2004 (a lentiviral vector encoding the functional COL7A1 gene), and expanded further. If the manufacturing process does not yield an FCX-007 cell count sufficient for at least one administration, or does not meet manufacturing release specifications, an additional set of biopsies may be requested from the subject.

For each subject, approximately will be manufactured for use in this study. Up to will be administered at each dose administration. Cells undergo release testing and sent to the Investigative Site for administration on Day 0. The duration between biopsy collection and completion of manufacturing is approximately 120 days (4 months) but can vary due to capacity, technical manufacturing reasons, or clinical protocol required pauses between subjects.

CONFIDENTIAL Page 23 of 75

Final Version 8.0, 29 Oct 2019

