### 7.3.1 Visit 2 (Wound Selection/Run-In)

Visit 2 procedures may occur up to 2 days (±1 day) prior to the day of FCX-007 administration. The following procedures will be performed during Visit 2:

- Re-evaluation of inclusion/exclusion criteria
- Review of medical and medication history
- Skin Exam
- Vital signs: blood pressure, heart rate, respiratory rate, temperature
- Collection of blood (approximately 12.5 mL) for laboratory tests
  - Serum chemistry
  - Hematology
- Collection of urine for pregnancy test, if applicable
- Bacterial culturing of target wounds
- Final target wound selections of up to 3 pairs from the selected potential target wounds (See Section **9.1** for details)
- Label the selected target wound pairs as T1A and T1B for the 1st pair, T2A and T2B for the 2nd pair, and T3A and T3B for the 3rd pair.
- Digital imaging of wounds.

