### 7.3.2 Visit 3 (Day 0; Day of Injection)

Visit 3 procedures are scheduled to occur on the day of receipt of FCX-007. The following procedures will be performed during this visit:

- Re-evaluation of inclusion/exclusion criteria
- Review of medical and medication history
- Physical and Skin Exam
- Vital signs: blood pressure, heart rate, respiratory rate, temperature
- Bacterial culturing of target wounds (may be done if clinical evaluation is

CONFIDENTIAL Page 31 of 75

indicative of infection)

- Surgical marking around the target wounds and on the intact skin
- Digital imaging of injection sites
- Tattoos will be placed on non-blistered skin near the target wounds for the purpose of calibrating the post-dose imaging.
- Tattoos will also be placed next to the intact skin injection sites for the purpose of precisely locating the biopsy sites at follow-up visits.
- Randomly assign each wound of a target wound pair to either active treatment or control (Visit 3 only).
- Biopsy collection to be used as IF/DIF and IEM.
  - Biopsy location markings must be imaged prior to collection.
  - Biopsy collection must occur prior to administration
- FCX-007 administration to target wounds
- FCX-007 administration to the intact skin.
- Post-dose digital imaging
- Post-dose assessment of concomitant medications and adverse events

As noted above, the subject may remain at the Investigative Site or in a nearby hotel for up to 2 days following FCX-007 administration. During this period, the subject will be monitored for autoimmune reactions to FCX-007. At a minimum, subjects will be contacted once per day on days in which there are no scheduled procedures.

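### No serum C7 antibody sample is scheduled between Screening and Week 4, so a seroconversion before dosing would first appear after dosing and could be misattributed to FCX-007

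*Combined protocol and SAP*

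**What the plan says.** Section 11.6.4 gives the sampling times for the serum assay: "Subject serum will be collected at Screening and Visits 5, 6, 8, and 10". Visits 7 and 9 are added only if held in the office. In Table 2 the C7 Antibody Assay row has no mark under Wound Monitoring, Day -2, Day 0 or Day 2.

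Exclusion 3 in section 4.2 is a criterion on the same kind of sample: "The presence of antibodies to the basement membrane of monkey esophagus by indirect immunofluorescence using the subject's serum". Sections 7.3.1 and 7.3.2 both list "Re-evaluation of inclusion/exclusion criteria", at Visit 2 (Day -2) and Visit 3 (Day 0). Visit 2 has a blood draw, "Collection of blood (approximately 12.5 mL) for laboratory tests", but the tests listed under it are serum chemistry and hematology. Visit 3 lists no blood draw.

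Section 6.1.1 puts manufacturing at about 120 days from biopsy. Section 3.1 says of the Wound Monitoring Period that "this period can extend beyond four months to accommodate patient scheduling, variations in manufacturing duration and protocol mandated delays". Section 3.4 adds: "The duration is about 20 months per subject, including the Screening, Wound Monitoring and Treatment Periods".

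Under section 11.6.4 a positive serum result must be recorded as an adverse event. Section 14.7.1 splits events into those before treatment and those that are treatment-emergent. Section 14.7.4 calls for a descriptive evaluation of C7 antibodies and names no baseline sample for them.

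**The concern.** Antibody to type VII collagen is the main immune safety signal for this product, and the plan treats pre-existing antibody as a real possibility: exclusion 3 exists, and prescreening (7.1.1) looks at antibody history. Yet the sample that would show a subject's serum status near the first dose is not scheduled. A subject who converts during manufacturing would first test positive at Week 4, after product has been given.

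The design offers little help in separating such a case from a product effect. Serum antibody is systemic, so the untreated control wound in each pair is uninformative, and there are no untreated subjects. Section 13.2 lets an event be graded possibly related when there is a temporal association and the product cannot be ruled out. Under 11.1.1 an autoimmune response graded at that level or higher temporarily suspends administration. Week 4 data also feed the DSMB reviews that release the staggered subjects (section 7) and inform the move to Phase II and to pediatric enrollment (11.1.2). With at most 12 subjects, or 13 if the optional seventh Phase II subject in 3.3 is enrolled, one misattributed positive could change the safety message.

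Other pre-dose tests are handled differently. Chemistry and hematology are repeated at Day -2, which is the reference for laboratory adverse events (11.6.1). Pregnancy is retested at Visit 2. The RCL baseline may be drawn at a wound monitoring visit, with the result required before Day 0 (7.2 and Table 2, footnote 7).

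**Working it through.** The plan states no figure to reproduce here. The check has two parts: the length of the unsampled interval, and what that interval could mean in numbers.

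**1. The interval**

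- Screening to Day 0: about 120 days (6.1.1), possibly longer (3.1).
- Day 0 to Week 4: 28 days.
- Screening to Week 4: 120 + 28 = 148 days.
- Share before any product: 120/148 = 81%.

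For a longer gap, section 3.4 gives about 20 months per subject and a 12-month treatment phase, leaving 20 − 12 = 8 months, or about 243 days. The share is then 243/(243 + 28) = 90%.

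If background conversion occurs at a constant rate, 81% to 90% of background conversions first seen at Week 4 would have happened before dosing. This needs no value for the rate.

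**2. Chance of at least one background conversion among 12 subjects**

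The documents give no background rate, so r per year is an assumed range. For a window of m months and 12 subjects,

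P = 1 − [(1 − r)^(m/12)]^12 = 1 − (1 − r)^m.

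| Assumed r per year | Before dosing, m = 4 | Before dosing, m = 8 | About four weeks after dosing, m = 1 |
|---|---|---|---|
| 1% | 1 − 0.99^4 = 3.9% | 1 − 0.99^8 = 7.7% | 1% |
| 2% | 1 − 0.98^4 = 7.8% | 1 − 0.98^8 = 14.9% | 2% |
| 5% | 1 − 0.95^4 = 18.5% | 1 − 0.95^8 = 33.7% | 5% |
| 10% | 1 − 0.90^4 = 34.4% | 1 − 0.90^8 = 57.0% | 10% |

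The m = 4 column is the part that a sample just before dosing would identify. The last column is ambiguity that remains even with such a sample.

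**3. Effect of the sampling point**

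A Visit 2 sample, nominally two days before dosing, cuts the ambiguous window from 148 to about 28 + 2 = 30 days. A sample at the last wound monitoring visit, which Table 2 places no more than 60 days before injection, cuts it to at most 60 + 28 = 88 days.

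**4. Blood volume**

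Visit 5 takes about 19 mL for chemistry, hematology, C7 antibody and RCL (7.3.4). Chemistry and hematology alone take about 12.5 mL (7.3.1), and RCL takes 5 mL (11.6.3). The remainder for C7 antibody is 19 − 12.5 − 5 = 1.5 mL. This is inferred from approximate volumes; no section states it.

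**The case against.** The strongest reply is that the plan leaves several routes open, and each limits the point.

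- **Discretionary draws.** Section 7.4 allows unscheduled blood draws. A reader might infer that exclusion 3 cannot be re-checked before dosing. The documents support only that no re-check is scheduled.
- **Wording of exclusion 3.** Exclusions 11 and 12 name Day -2 and Day 0; exclusion 3 names no time point. HIV and hepatitis, behind exclusion 2, are also tested only at Screening. A reader might infer that a subject who converts would be dosed in breach of exclusion 3. The text does not settle that, because it does not say whether re-evaluation requires a fresh result.
- **Attribution.** A reader might infer that a background conversion automatically counts as a product effect. It does not. The investigator grades relatedness on five levels, the suspension rule depends on that judgment, the DSMB can lift a suspension, and the antibody analysis is descriptive.
- **Day 0 DIF.** The biopsy is taken before administration (7.3.2) and DIF is repeated in follow-up (10.2.4), where the immune assessment draws on all the assays. A positive Day 0 DIF would point to an origin before dosing, so not every pre-dose conversion need look treatment-emergent.
- **The rate.** Nothing in the documents shows that background conversion occurs at a rate that matters.

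All of this stands as a limit on the claim; none of it closes the gap. A discretionary draw is not a planned baseline. DIF is a tissue assay rather than the serum test in exclusion 3, and no section requires its result before dosing. Relatedness is harder to judge when the last serum result is four months old.

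**Conclusion.** The point holds as a scheduling gap that weakens attribution. No serum C7 antibody sample is planned between Screening and Week 4. The re-evaluation of exclusion 3 at Visits 2 and 3 therefore rests on a result about four or more months old unless a discretionary draw is made, and a conversion in that time would surface only after dosing.

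The firmest figure is the 81% of the interval that precedes any product, which rests on the stated 120 days. The chances of about 4%, 8%, 19% and 34% rest on assumed rates, 12 subjects, independence between subjects and a four-month gap. They illustrate the risk and do not estimate it.

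A reader might take the whole five months from Screening to Week 4 and quote about 5%, 10%, 23% and 41% (1 − (1 − r)^5 for the same rates). That overstates what can be gained, because it includes the weeks after dosing, where about 1%, 2%, 5% or 10% remains whatever is done before dosing.

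The study is exploratory and the analysis descriptive, so no formal inference is at risk. The case for change is that a small addition would make the main immune safety signal easier to interpret at the Week 4 DSMB reviews.

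**What to change.** 1. Add serum for the same indirect-IF assay to the existing Visit 2 draw, and mark it in Table 2, 7.3.1 and 11.6.4. The last wound monitoring visit is an alternative, as the RCL baseline already allows; it gives more time for a result but leaves a longer window before dosing.
2. If turnaround is too slow for a result before Day 0, store the sample and run it beside the Week 4 sample. That resolves attribution but does not inform the eligibility re-evaluation.
3. In 14.7.4, name this sample as the baseline for treatment-emergent C7 antibody, and report conversions from Screening to baseline separately from those after dosing.
4. Reconcile the re-evaluation of exclusion 3 at Visits 2 and 3 with the sampling schedule: state which result it relies on, and whether a current one must be available before Day 0. That decision is the sponsor's.

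The cost is about 1.5 mL more blood (inferred above) and one more assay per subject, with an assay the study already uses. At Visit 2 it needs no extra visit or needle stick.

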## 12 Procedures: Optional Diagnostic Assessments

The following procedures, specific to confirming a subject's diagnosis of RDEB, are performed only under the condition that they have not been conducted and documented previously as determined during Prescreening. If needed, the following procedures are conducted during the Screening Visit.

## 12.1 Evaluation of Diagnostic Biopsies

If not conducted previously, two biopsies are obtained during the Screening Visit for the purpose of conducting IF and IEM evaluations as outlined in Sections **10.1** and **10.2.2**.

## 12.2 Genetic Testing

This process is only applicable to potential subjects which are eligible for the study but do not have genotype information. Genetic testing is conducted on the subject to confirm that the subject has RDEB as well as for determination of NC1 status.

The subject is asked to have a blood sample drawn in a laboratory that is convenient for them. This blood sample will be sent to an outside lab for genetic testing. All fees associated with this genetic testing are reimbursed.

## 12.3 Autoimmune Assay

If not conducted previously, a biopsy is obtained during the Screening Visit for the purpose of performing DIF. Reference Section **10.2.4 Autoimmune Assays.** 

CONFIDENTIAL Page 54 of 75

Fibrocell Technologies RDEB Phase I/II Protocol Final Version 8.0, 29 Oct 2019

#### 13 **Adverse Experiences**

#### 13.1 Definitions

#### 13.1.1 Adverse Events

An Adverse Event (AE) is any untoward medical occurrence in a clinical investigation subject administered a pharmaceutical product and which does not necessarily have a causal relationship with this treatment. An AE can therefore be any unfavorable and unintended sign (including an abnormal laboratory finding), symptom, disease or exacerbation of a pre-existing condition temporally associated with the use of a medicinal (investigational) product.

Subjects should be asked a non-leading question in order to avoid bias in eliciting AEs; such as "How are you feeling?" It is important to question the subject in a non-leading way about changes in their health or concomitant medication usage since their last visit. Where possible, a diagnosis rather than a list of symptoms should be recorded. If a diagnosis has not been made then each symptom should be listed individually.

Each AE requires a complete description including date of onset and corrective actions taken. The intensity of the AE and its relationship to the investigational product, as well as its outcome, must be recorded in the CRF.

Symptoms of the disease under study/lack of efficacy should not be considered as AEs, as long as they are within the normal day-to-day fluctuation or expected progression of the disease. However, significant worsening of the symptoms should be recorded as an AE.

A change in the value of a safety laboratory evaluation can represent an AE if the change is clinically relevant (as determined by the Investigator) or if, during treatment with the investigational product, a shift of a parameter is observed from a normal value to a pathological value, or a further worsening of an already pathological value. When evaluating such changes, the extent of deviation from the reference range, the duration until return to the reference range, either while continuing treatment or after the end of treatment with the investigational product, and the range of variation of the respective parameter within its reference range, should be taken into consideration. The Investigator should decide, based on the above criteria and the clinical condition of a subject, whether a change in a laboratory parameter represents an AE. For pathological laboratory values that were not present at baseline, follow-up laboratory evaluations should be performed until the values return to within reference range or until a plausible explanation is found.

AEs should be recorded, starting from subject enrollment (date of signature on informed consent) per the Schedule of Events, until the end of the Long Term Follow-Up Period, and are to be recorded on the appropriate AE pages in the CRF and in source documents. Where possible, all AEs should be followed to resolution, or an outcome is reached. Medical tests and examinations will be performed, as appropriate, to document resolution of event(s).

CONFIDENTIAL Page 55 of 75 Fibrocell Technologies RDEB Phase I/II Protocol Final Version 8.0, 29 Oct 2019

**NOTE:** Blistering MUST be noted as an AE if it is seen proximal to a product-treated wound.

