# 3 Experimental Plan

### 3.1 Study Design

This is a Phase I/II Study of FCX-007 (Genetically-Modified Autologous Human Dermal Fibroblasts) for Recessive Dystrophic Epidermolysis Bullosa (RDEB) being conducted by Fibrocell to evaluate FCX-007 in subjects with RDEB. Up to twelve subjects will be enrolled, up to six (6) in Phase I, and up to six (6) in Phase II. Phase I will enroll adult subjects only; Phase II can enroll adults and pediatric subjects (aged seven (7) or older). Within Phase I, subjects will be assigned to one of two arms: subjects with NC1+ status will be enrolled into Arm A and subjects with NC1- status will be enrolled into Arm B. The arms will enroll independently. In Phase I, the study may enroll an equivalent number of subjects to Arm A and Arm B (n=3 each arm). In Phase II, the study will target enrolling 3 subjects to each arm, but will allow a disproportionate distribution of subjects between Arm A and Arm B to equal 6 total subjects.

Figure 2 - High-Level Study Design

One administration of FCX-007 will consist of up to sixty (60) 0.25 mL intradermal injections in wounded and/or intact skin. The majority of the injections will be administered around the margin of target wounds and at least 6 injections will be administered to intact skin. The Investigator will attempt to administer all 15mL of FCX-007. This will be accomplished by selecting target wounds that are as close as possible to 54 linear cm, leaving at least 6 administrations for intact skin, for a total of 60 injections.

For the wound administrations, subjects will receive FCX-007 administered intradermally to one, two or three paired target wounds at Visit 3 (Day 0). Subjects will receive a second administration to wounded and/or intact skin at Visit 5 (Week 4).

In this study, one wound in each target wound pair will be used as a control for efficacy and safety evaluations. FCX-007 administered wounds will be compared within paired target wounds to untreated wounds.

CONFIDENTIAL Page 17 of 75

Final Version 8.0, 29 Oct 2019

As there is no previous human experience with FCX-007, treatment administration will be staggered in two places:

- 1. Between the first and second enrolled subjects in each arm.
- 2. Between the third and fourth enrolled subjects in each arm.

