## 11 Procedures: Safety Assessments

Timing of safety assessments must be performed in accordance with **Table 2 - Schedule of Events**. Safety assessments include evaluation of medical and medication history, physical / skin examination, vital signs, AEs, and laboratory evaluations. AEs will be captured between visits through use of an Adverse Event Diary. Post-administration changes in these assessments that are deemed to be clinically significant by an Investigator or Sub-Investigator will be assessed as AEs.

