#### 13.2.1 Post-FCX-007 Administration Adverse Event Monitoring

The Investigator must monitor the subject's wounds closely for additional blister formation and expansion of the border of the wound during injections and immediately post-administration up to the 2 day follow up visit. Additional blister formation and/or expansion of the border of the wound must be recorded as an adverse event.

CONFIDENTIAL Page 57 of 75

Fibrocell Technologies RDEB Phase I/II Protocol Final Version 8.0, 29 Oct 2019

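### Blistering is an unconditional adverse event only near the treated wound, not near its safety-control wound; separately, the plan gives conflicting starting points for AE recording

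*Combined protocol and SAP*

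**What the plan says.** **Role of the untreated wound.** Section 3.1, repeated in the synopsis, states that "one wound in each target wound pair will be used as a control for efficacy and safety evaluations" and that "FCX-007 administered wounds will be compared within paired target wounds to untreated wounds".

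**Blistering as an AE.** Section 13.1.1 has a note: "Blistering MUST be noted as an AE if it is seen proximal to a product-treated wound". The general rule in the same section is that "Symptoms of the disease under study/lack of efficacy should not be considered as AEs" while they stay within ordinary variation or the expected course of the disease. It adds: "However, significant worsening of the symptoms should be recorded as an AE". Section 11, whose safety assessments include the skin examination, says "Post-administration changes in these assessments that are deemed to be clinically significant by an Investigator or Sub-Investigator will be assessed as AEs". Section 13.2.1 tells the investigator to "monitor the subject's wounds closely for additional blister formation and expansion of the border of the wound during injections". The period that it sets then continues, in its own terms, "immediately post-administration up to the 2 day follow up visit"; new blisters or border expansion in that window must be recorded as AEs.

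**Reporting.** Section 14.7.1 tabulates AEs by term, body system, phase, relationship, seriousness and severity. It does not name a split by treated and untreated wound. Section 14.2 provides in general for summaries by treatment regimen and for counts of subjects or wounds.

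**Start of AE recording.** Section 13.1.1 starts at the consent signature but refers to the Schedule of Events. In that schedule (Table 2) the AE row is first marked at Visit 3, and Section 7.3.2 lists the AE assessment there as post-dose. Section 13.2 requires CRF reporting of AEs after FCX-007 administration. Section 13.1.2 collects SAEs from enrollment. Section 14.7.1 plans a pre-treatment AE group beside the treatment-emergent one.

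**The concern.** Safety is the primary objective, and blistering is the core feature of RDEB (Section 1.1). With up to 12 subjects, the randomised within-subject pair is the natural way to tell background blistering from a local effect of the product. That works only if the rule for recording a blister does not depend on which wound was injected. Here it does, and the investigator knows which wound that was. The DSMB also considers adverse events when it recommends whether to proceed to Phase II (Section 11.1.2).

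The second issue is independent of the first. An analysis group is planned for pre-treatment AEs, but the visit schedule does not provide for collecting the non-serious ones. The period concerned includes the manufacturing biopsies.

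**Working it through.** The plan gives no figure on this point, so the check is mainly a comparison of its passages.

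**1. Recording rule within one pair**

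| Source | Treated wound | Untreated wound |
|---|---|---|
| 13.1.1, blister note | Always an AE, no time limit | Not named |
| 13.1.1, disease symptoms | Overridden by the note | AE on significant worsening |
| 11, safety assessments | Overridden by the note | AE if judged clinically significant |
| 13.2.1, post-injection window | AE | AE only if the section covers all wounds |

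**2. Scope of 13.2.1.** Its reference to the subject's wounds suggests every wound; its reference to the time of injection suggests injected wounds. On the narrow reading the difference in rules has no exception. On the wide reading it is suspended only within the window.

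**3. The window after the second administration.** The only 2-day visit is Visit 4, which follows Visit 3 (Section 7.3.3). Table 2 has no visit between Week 4 and Week 12, so the end of the window is undefined for the Week 4 administration. The consequence is limited, because blistering near a treated wound stays mandatory under 13.1.1. Only border expansion and, on the wide reading, control-wound blistering depend on this.

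**4. Direction of any bias.** Let R be the true treated-to-control ratio of blistering. Assume that treated-wound blisters are all recorded, as required, and let q be the share of control-wound blisters that are recorded. Setting the 13.2.1 window aside:

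expected recorded ratio = R / q, with q at most 1.

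The recorded ratio cannot fall below R, so the lean is against FCX-007. If q = 1 there is no bias. The documents give no basis for q, and I assume no value. Two things raise it: sites may record more than they must, and paired wounds may lie close together (Section 9.1.1), so that some blisters near a control are also near a treated wound.

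**5. AE start point**

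| Source | Start implied |
|---|---|
| 13.1.1 | Consent, by reference to Table 2 |
| Table 2, AE row | Visit 3 |
| 7.3.2 (Visit 3) | Post-dose |
| 7.1.3, 7.2, 7.3.1 (Visit 1, wound monitoring, Visit 2) | No AE assessment listed |
| 13.2 | CRF reporting after administration; earlier recording not excluded |
| 13.1.2 (SAEs only) | Enrollment |
| 14.7.1 | Needs pre-treatment AEs |

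Table 2 has three columns from consent to just before Day 0: Visit 1, Wound Monitoring and Visit 2. All three have a skin examination mark and none has an AE mark. Manufacturing alone takes about 120 days (Section 6.1.1). Section 3.4 implies about 20 − 12 = 8 months before treatment. These are calendar lengths, not counts of lost events.

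**The case against.** The mandatory rule at the injected site can be read as deliberate extra surveillance in a first-in-human study, and any lean it causes is conservative. No treated-versus-untreated AE table is named in 14.7.1, so the bias would affect a comparison that is permitted but not specified. Both wounds are imaged and measured alike (Section 9.3), skin is examined at all site visits (Section 11.4), and the investigator rates each AE for relationship. The AE diary captures events between visits. For the start point, SAEs are covered from enrollment, history is updated at Visits 2 and 3 (Section 11.2), and the Safety Population contains only dosed subjects.

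Most of this stands and lowers the weight of the point. It does not remove it. The diary does not make the AE threshold equal for the two wounds. Imaging and skin examination are symmetric, but the step from an observed blister to an AE is not. If the general wording of 14.2 is applied to AEs, it yields the unequal comparison; if it is not, the safety-control role has no AE summary behind it.

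Several stronger readings are tempting, and the documents do not support them:

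- **That control-wound blisters may not be recorded.** Nothing forbids it.
- **That harm could be hidden, or a stopping decision distorted.** Recording is mandatory on the treated side, and no suspension trigger in Section 11.1.1 uses a within-pair comparison.
- **That the number of visits, or the gap after Week 4, measures lost events.** The diary covers the time between visits, and the 13.1.1 note has no time limit.
- **That Section 13.2 bars pre-dose AEs.** It requires reporting after administration and is silent on earlier events.

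**Conclusion.** Both parts hold as matters of wording and reporting, at a level worth considering.

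**Blistering.** The rule differs within a randomised pair, although the untreated wound is named as a safety control. Any summary of blistering AEs by wound would lean against FCX-007 to the extent that control-wound blisters go unrecorded. The size is unknown and may be zero. The direction rests on treated-wound blisters being recorded as required.

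**Start point.** Section 13.1.1 cites a schedule that contradicts it. If sites follow Table 2, the pre-treatment AE group would hold essentially only SAEs, with the history updates as partial cover. If they follow 13.1.1, the group can be filled, but the visit lists do not prompt for it. Treatment-emergent results are not affected on either reading.

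**What to change.** **Blistering**

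- Keep the treated-wound rule in 13.1.1, and apply the same blister-recording rule over the same window to both wounds of every target pair.
- Record the target wound label (T1A, T1B and so on) on each local AE, using the nearest wound where the pair lies close together.
- State in 13.2.1 whether it covers injected wounds or all target wounds, and reconcile its 2-day visit with Table 2 for the Week 4 administration.
- Add to 14.7.1 a descriptive display of local wound events by treated versus untreated wound.

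**Start point**

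- Reconcile 13.1.1, 13.2, the Section 7 visit lists and Table 2 to one AE start point that is consistent with the pre-treatment group in 14.7.1.

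**Cost.** The changes are to wording, one table, and a wound label on the AE form if it does not already have one (the CRF is not among the documents). No new wound examination is needed at existing visits. The real downside is more AE entries, possibly many in a disease of repeated blistering.
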